11.4.2 Primary Analysis

The primary analysis will be a repeated measures ANOVA of SRRS scores with two timepoints (within

subjects: baseline and week 3) and four groups (lf-rTMS, iTBS, sham, waiting group-If-rTMS). In case of significant baseline demographic or clinical group differences, we will adjust for these in an repeated measures ANCOVA of SRRS.

The analysis will be performed by the PI and his team in SPSS using data from the RedCap database.

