Study Duration:	
Total study duration will be 4 years. Total duration of participant recruitment will be 3 years.

Study Schedule:	
Planned 03/2019 of First-Participant-In Planned 06/2022 of Last-Participant-Out

Investigator(s):	
- see Sponsor-Investigator

Study Centre(s):	
Single-centre trial at the University Hospital of Psychiatry, Bern

Statistical Considerations:	
The main effects of the 3-week interventions on PS (SRRS scores) will be calculated in a repeated measures design including 2 measures (Baseline, week 3) and four groups (lf-rTMS, iTBS, sham, waiting group-lf-rTMS). Assuming a moderate effect size ($f = 0.23$) as indicated by our pilot data in a repeated measures ANOVA with moderate correlation between time points (0.5), a power of 0.95 and an alpha = 0.05, we would need 88 patients (22 per group).

GCP Statement:	
This study will be conducted in compliance with the protocol, the current version of the Declaration of Helsinki, the ICH-GCP or ISO EN 14155 (as far as applicable) as well as all national legal and regulatory requirements.

ABBREVIATIONS

AE	Adverse Event
BASEC	Business Administration System for Ethical Committees, (https://submissions.swissethics.ch/en/)
BNSS	Brief Negative Symptom Scale
CA	Competent Authority (e.g. Swissmedic)
CEC	Competent Ethics Committee
CRF	Case Report Form
ClinO	Ordinance on Clinical Trials in Human Research (in German: KlinV, in French: OClin, in Italian: OSRUm)
eCRF	Electronic Case Report Form
CTCAE	Common terminology criteria for adverse events
DSUR	Development safety update report
GCP	Good Clinical Practice
IB	Investigator's Brochure
Ho	Null hypothesis
H1	Alternative hypothesis
HRA	Federal Act on Research involving Human Beings (in German: HFG, in French: LRH, in Italian: LRUm)
IMP	Investigational Medicinal Product
IIT	Investigator-initiated Trial
ISO	International Organisation for Standardisation
iTBS	Intermittent Theta Burst Stimulation
ITT	Intention to treat
MD	Medical Device
MedDO	Medical Device Ordinance (in German: MepV, in French: ODim)
PANSS	Positive And Negative Syndrome Scale
PI	Principal Investigator
PS	Psychomotor Slowing
rTMS	Repetitive Transcranial Magnetic Stimulation
SAE	Serious Adverse Event
SDV	Source Data Verification
SMA	Supplementary Motor Area
SOP	Standard Operating Procedure
SPC	Summary of product characteristics
SRRS	Salpêtrière Retardation Rating Scale
SOFAS	Social and Occupational Functioning Scale

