3.1.7 Brain stimulation for psychomotor slowing

Repetitive transcranial magnetic stimulation (rTMS) temporarily alters brain function in the targeted cortical areas. In addition, distant effects occur due to changes in network properties⁶⁹. Depending on the frequency and type of stimulation, distinct effects on brain function are expected. Low-frequency rTMS (**If-rTMS**) and continuous theta burst stimulation (cTBS) have **inhibitory** effects, while high-frequency rTMS (hf-rTMS) and intermittent theta burst (**iTBS**) have **facilitatory** effects. The preliminary knowledge of the pathobiology of PS suggests that rTMS could improve PS by changing aberrant motor network connectivity. Still, there are no published reports on the effects of non-invasive brain stimulation on PS. However, my group is conducting a randomized, double-blind, sham-controlled trial of rTMS for psychomotor slowing in major depressive disorder and schizophrenia (**NCT03275766**, clinicaltrials.gov). Treatment is based on rTMS in 4 arms: 1) facilitatory hf-rTMS over the left dorsolateral prefrontal cortex (DLPFC), 2) inhibitory If-rTMS over the supplementary motor area (SMA), 3) facilitatory iTBS over the SMA, and 4) sham stimulation with a placebo coil. The primary outcome parameter is the percentage of responders (> 30% reduction in the Salpêtrière Retardation Rating Scale (SRRS) from baseline). Across the whole group of 34 randomized subjects (22 with schizophrenia and 12 with depression), there is a group difference in the number of responders after 15 rTMS sessions applying the last-observation-carried-forward method ($\text{Chi}^2=11.3$, $\text{df}=3$, $p=.007$) with **78% responders under If-rTMS over SMA and no responder under iTBS over SMA**. When we exclusively focus on schizophrenia, this effect is also detected ($\text{Chi}^2=6.6$, $\text{df}=3$). Thus, If-rTMS over SMA ameliorates PS.

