3.6 Explanation for choice of comparator (or placebo)

This study will have two comparators: one placebo stimulation and an active stimulation that produces the opposite effect of the investigated protocol, i.e. iTBS over SMA which will facilitate neural activity. Both comparators are necessary to demonstrate clinical utility (placebo) and the neurophysiological changes associated with the three treatments (placebo and iTBS). Only this approach will finally allow testing whether inhibitory lf-rTMS is changing the motor system in a specific direction that is causal for clinically relevant changes of motor behavior. The waiting list will disentangle specific stimulation effects from effects of time or expectation. Placebo will disentangle specific rTMS treatment effects. Finally, iTBS will disentangle the direction of neurophysiological changes of the motor system. All stimulations will target the left SMA. Mode of application, localization, frequency of sessions and apparatus will be identical for all protocol arms. Arms will differ in the coil used (real or sham) and in the frequency of the applied stimulation (1 Hz vs. iTBS). The number of pulses is similar in all protocols (1'000-1'200).

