11.1 Hypotheses

Aim 1: investigate the clinical and functional neural changes following 15 sessions of daily rTMS

Hypothesis 1a (main hypothesis): lf-rTMS (inhibitory) will be superior over placebo or iTBS (facilitatory) in all clinical and motor behavioral measures, e.g. greater reduction in SRRS scores from baseline, greater increase in activity levels, or coin rotations.

Hypothesis 1b: lf-rTMS will reduce aberrant functional connectivity in the motor system, e.g. between thalamus and M1. lf-rTMS will alter regional CBF in the motor system and increase SMA and M1 activity during the fMRI task. No relevant changes are expected in the sham group, iTBS may deteriorate neural alterations.

Hypothesis 1c: cortical excitability will be differentially changed with rTMS. Lf-rTMS will increase SIC1, while iTBS will reduce SIC1.

Aim 2: characterization of psychomotor slowing (PS) in schizophrenia spectrum disorders compared to healthy controls

Hypothesis 2a: Patients will have poorer performance on all motor tasks, eg. reduced activity levels, increased postural sway, and less coin rotations

Hypothesis 2b: Patients will have aberrant structural and functional connectivity within the motor system, as well as increased CBF in basal ganglia and decreased CBF in premotor/motor cortex. Applying network metrics, the functional motor network will be less efficient in schizophrenia.

Hypothesis 2c: Behavioral measures of PS will be associated with aberrant motor network structure, perfusion, function, and connectivity. For example, patients with strong PS will have increased resting state functional connectivity between thalamus and M1. PS severity will be linked to reduced structural motor network efficiency, lower M1 and SMA activity during the fMRI task, and increased SMA perfusion at rest.

Hypothesis 2d: Patients will have increased motor cortex excitability (e.g. reduced SICI), which will be linked to measures of PS.

Aim 3 characterize short term dynamics of PS

Hypothesis 3a: in very few subjects we expect relevant spontaneous improvements in PS measures. The majority will have less than 20% fluctuation of motor parameters within 3 weeks

Hypothesis 3b: we expect slight longitudinal changes in resting state functional connectivity and perfusion of the motor system, but no structural changes.

Aim 4: to describe the short-term and medium-term clinical outcome of 3 weeks of rTMS intervention

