11.2 Determination of Sample Size

The main effects of the 3-week interventions on PS (SRRS scores) will be calculated in a repeated measures design including 2 measures (Baseline, week 3) and four groups (If-rTMS, iTBS, sham, waiting group-If-rTMS). Assuming a moderate effect size ($f = 0.23$) as indicated by our pilot data in a repeated measures ANOVA with moderate correlation between time points (0.5), a power of 0.95 and an $\alpha = 0.05$, we would need 88 patients (22 per group).

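### The primary test is a four-group omnibus ANOVA with no named contrast, so a significant result does not by itself support the main hypothesis that lf-rTMS beats placebo or iTBS

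*Combined protocol and SAP*

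**What the plan says.** Section 11.4.2 defines the primary analysis: "The primary analysis will be a repeated measures ANOVA of SRRS scores with two timepoints" and four groups (lf-rTMS, iTBS, sham, waiting group). The synopsis agrees: the effects "will be calculated in a repeated measures design including 2 measures (Baseline, week 3") and the same four groups. Neither place names a model term, a contrast, a testing order or a multiplicity rule.

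The main hypothesis, 1a in section 11.1, is pairwise and directional: "lf-rTMS (inhibitory) will be superior over placebo or iTBS (facilitatory) in all clinical and motor behavioral measures". Section 5.1 sets the endpoint as SRRS change from baseline to week 3.

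The comparators have different roles. Section 3.6 says: "Both comparators are necessary to demonstrate clinical utility (placebo) and the neurophysiological changes associated with the three treatments (placebo and iTBS"), and of the fourth arm: "The waiting list will disentangle specific stimulation effects from effects of time or expectation". Section 6.1 relies on placebo to show that add-on rTMS has an effect, and notes that the waiting group is not completely blinded.

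Section 11.2 assumes f = 0.23, "as indicated by our pilot data in a repeated measures ANOVA with moderate correlation between time points (0.5"), with power 0.95 and alpha 0.05, and concludes "we would need 88 patients (22 per group"). Section 11 applies a two-sided 5% level to every analysis and promises effect sizes for between-group comparisons. Section 11.4.3 says that the secondary analyses address the hypotheses.

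**The concern.** The planned test and the main hypothesis ask different questions. Hypothesis 1a concerns lf-rTMS against two named comparators. The omnibus term asks only whether any of the four arms differ in SRRS change. It can reject because unblinded waiting patients do worse than everyone else, or because iTBS alone moves, with no difference between lf-rTMS and placebo.

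The main claim would then rest on follow-up comparisons whose pair, order and error control are not fixed in advance. Hypothesis 1a joins placebo and iTBS with 'or', which leaves open whether one or both must be beaten. The single power figure also belongs to the omnibus test, so a reader cannot tell how well the trial is powered for the comparison on which sections 3.6 and 6.1 rest clinical benefit.

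**Working it through.** **Inputs.** From 11.2: f = 0.23, correlation 0.5, m = 2 measures, k = 4 groups, N = 88 (22 per arm), alpha 0.05. The documents give no SRRS SD and no expected mean by arm, so every gap and pattern below is an assumption. Gaps are in units of the within-arm SD of change. No dropout is assumed.

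**1. The plan's own figure.** For group by time, lambda = f² × N × m / (1 − rho) = 0.0529 × 88 × 2 / 0.5 = 18.62, with df 3 and 84. Power is 0.957. The smallest N for 0.95 is 86, which becomes 88 with equal arms, so the figure reproduces. Other standard readings do not give 88: the time main effect needs 64, and the group main effect needs 248 (power 0.512 at 88). Section 11.2 speaks of main effects and never of an interaction. That 0.95 refers to the interaction is therefore an inference, made because no other standard variant returns 88.

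**2. Omnibus rejection when lf-rTMS equals placebo.** If one other arm differs by g, lambda = 22 × g² × 3/4, with df 3 and 84.

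| g | lambda | P(omnibus significant) |
|---|---|---|
| 0.3 | 1.485 | 0.15 |
| 0.5 | 4.125 | 0.35 |
| 0.8 | 10.56 | 0.76 |

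**3. Power for lf-rTMS versus placebo at the same f.** On the change scale, the SD of the four mean changes is √(0.0529 × 2 / 0.5) = 0.46. Each pattern is scaled to that value. Power is from the noncentral t with noncentrality d × √(22/2), df 42, two-sided 0.05.

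| Assumed pattern | d, lf-rTMS vs placebo | Power |
|---|---|---|
| lf-rTMS best, placebo worst, others midway | 1.30 | 0.99 |
| only lf-rTMS differs | 1.06 | 0.93 |
| lf-rTMS and iTBS equally better than the other two | 0.92 | 0.85 |
| lf-rTMS best, iTBS worst, others midway | 0.65 | 0.56 |

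With 22 per arm, the contrast has power 0.80 at d = 0.865 and 0.95 at d = 1.11.

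**4. False positives in follow-up tests.** Simulation, 22 per arm, one final analysis, only the waiting arm differing, by 0.3, 0.5, 0.8 or 1.062:
- Omnibus significant, then only lf-rTMS vs placebo tested: 0.027, 0.038, 0.048, 0.050.
- Omnibus significant, then lf-rTMS vs placebo and vs iTBS both tested unadjusted, either significant: 0.048, 0.068, 0.087, 0.090. About half of these favour lf-rTMS (0.024 to 0.045, against 0.025 for one planned two-sided contrast).
- Fixed order starting with lf-rTMS vs placebo: 0.050 at every gap.

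**5. What the pilot results can settle.** Section 3.1.7 reports "78% responders under If-rTMS over SMA and no responder under iTBS over SMA". It gives no sham rate, and that trial's remaining arm was high-frequency stimulation over the DLPFC, not a waiting list. It cannot show which pattern in step 3 applies.

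**The case against.** The strongest defence is that the four-group ANOVA matches objective 4.2, which compares lf-rTMS with iTBS, placebo or a waiting list, and that follow-up comparisons are plainly foreseen in sections 11 and 11.4.3. The omnibus test also gives some protection. If only lf-rTMS versus placebo is tested after it, the false-positive rate stays at or below 0.05. The rejections in step 2 are correct rejections of the omnibus null and do harm only if read as an answer to 1a.

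All of this stands, and it limits the size of the problem. It does not remove it: foreseeing comparisons is not the same as fixing which one decides, and the protection weakens once a second pair is tested unadjusted.

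A reader might go further and infer that the sample size is wrong, or that the key comparison is underpowered. The documents support neither. The 88 is correct on its own inputs, and f = 0.23 does not determine the lf-rTMS versus placebo gap: under some patterns its power exceeds 0.95, under others it falls well below.

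**Conclusion.** The concern holds and should be fixed. It does not invalidate the design. A significant primary result, obtained exactly as planned, would not by itself support hypothesis 1a. Under the assumed gaps, the omnibus term rejects in 15% to 76% of trials where lf-rTMS equals placebo. The excess error is modest: at most about 0.09 with two unadjusted pairs when only the waiting arm differs.

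A reader might infer serious inflation of the error rate from this point alone; those figures do not show it. They do assume a single final analysis. Section 11.4.4 allows optional interim analyses of the primary analysis after 10 to 70 subjects. The rates above hold only if no decisions are taken on those, and naming a contrast does not address them. Power for the key comparison is unstated, and nothing here shows that it is low.

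**What to change.** In 11.4.2 and the synopsis, make the lf-rTMS minus placebo difference in SRRS change from baseline to week 3 (two-sided 0.05) the primary contrast. Follow it in fixed order with lf-rTMS versus iTBS, then lf-rTMS versus waiting list, noting that the last group is not completely blinded. This covers every comparison in objective 4.2. Keep the four-group group-by-time ANOVA as supportive. Placebo first follows from 3.6 and 6.1; the sponsor may justify another order, provided it is prespecified.

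In 11.2, name the term to which the 0.95 refers. Add that 22 per arm gives the contrast power 0.80 at d = 0.865 and 0.95 at d = 1.11, in SD of change and without dropout.

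The change is one of wording. Its downsides are that the stated power for the key comparison may look less favourable than 0.95, and that later comparisons are tested only if earlier ones succeed. Whether 22 per arm is enough for the contrast depends on the gap the sponsor expects, which the documents do not give.

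Requiring both the placebo and the iTBS contrast to succeed is not recommended as the default. Compared with lf-rTMS versus placebo alone, it lowers the chance of success from 0.93 to 0.88 if only lf-rTMS differs, from 0.99 to 0.56 if placebo is worst, and from 0.85 to about 0.04 or less if lf-rTMS equals iTBS. It makes no difference (0.56 either way) if iTBS is worst.

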5. STUDY OUTCOMES

5.1 Primary Outcome

The primary outcome variable is the SRRS score as a surrogate marker of psychomotor slowing. The primary endpoint will be the change SRRS ratings from baseline to week 3 measured with the SRRS⁹². The SRRS is administered at baseline, week 1, week 2, week 3, week 6, and week 24. It is an observer rated scale quantifying the severity of psychomotor slowing with 15 items, each ranging 0-4. The SRRS has been developed to target this behavior and has been used in previous trials. Assessments will be performed by blinded raters, who have been trained to use the scale reliably.

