7.1 Eligibility criteria

Participants fulfilling all of the following **inclusion** criteria are eligible for the study:

- ages 18–60 years
- Right-handed subjects
- Ability and willingness to participate in the study
- Ability to provide written informed consent
- Informed Consent as documented by signature (Appendix Informed Consent Form)

- **Patients only:** schizophrenia spectrum disorders according to DSM-5 **with** psychomotor slowing (SRRS score ≥ 15)

The presence of any one of the following **exclusion** criteria will lead to exclusion of the participant:

- Substance abuse or dependence other than nicotine
- Past or current medical or neurological condition associated with impaired or aberrant movement, such as brain tumors, stroke, M. Parkinson, M. Huntington, dystonia, or severe head trauma with subsequent loss of consciousness.
- Epilepsy or other convulsions
- History of any hearing problems or ringing in the ears
- Standard exclusion criteria for MRI scanning and TMS; e.g. metal implants, claustrophobia
- Patients only: any TMS treatment in the past 3 months
- Women who are pregnant or breast feeding,
- Intention to become pregnant during the course of the study,
- Female participants who are surgically sterilised / hysterectomised or post-menopausal for longer than 2 years are not considered as being of child bearing potential.
- Previous enrolment into the current study,
- Enrolment of the investigator, his/her family members, employees and other dependent persons
- **Controls only:** history of any psychiatric disorder or first-degree relatives with schizophrenia spectrum disorders.

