11. STATISTICAL METHODS

A two-tailed p-value of $< .05$ is considered to be statistically significant in all analyses. We will also report effect sizes for the comparisons of primary and clinical secondary outcome variables between groups.

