11.4.4 Interim analyses

Interim analyses of the primary analysis are planned after enrolment of 10, 20, 30, 40, 50, 60, and 70 subjects. The scope is to estimate whether any adjustments of the treatment arms are necessary. In addition, baseline data can be tested for associations between neuroimaging data and clinical/motor measures after enrolment of 20, 40, or 60 subjects.

All interim analyses are optional and at the discretion of the PI. Interim analyses are conducted by the PI and his team.

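### The primary SRRS model omits baseline SRRS as a planned covariate and adds covariates only when unlisted baseline tests turn out significant

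*Combined protocol and SAP*

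**What the plan says.** - Section 5.1 defines the endpoint: "The primary endpoint will be the change SRRS ratings from baseline to week 3".
- Section 11.4.2 gives the model: "The primary analysis will be a repeated measures ANOVA of SRRS scores with two timepoints (within", continuing "subjects: baseline and week 3) and four groups". Baseline SRRS is therefore one level of the outcome, not a covariate.
- The only provision for covariates is the next sentence of 11.4.2: "In case of significant baseline demographic or clinical group differences, we will adjust for these in an repeated measures ANCOVA of SRRS". It names no variables. The only threshold that could apply is the general two-tailed .05 of section 11, which "is considered to be statistically significant in all analyses".
- Section 11.2 sizes the trial on the same unadjusted model, with f = 0.23, alpha 0.05, power 0.95 and 22 patients per arm, using a "repeated measures ANOVA with moderate correlation between time points (0.5"). No SRRS standard deviation is given at either visit.
- Section 7.1 requires patients to have "psychomotor slowing (SRRS score ≥ 15").
- Section 11.4.4 adds: "Interim analyses of the primary analysis are planned after enrolment of 10, 20, 30, 40, 50, 60, and 70 subjects". These looks are optional, at the principal investigator's discretion, and are run by the team that also performs the final primary analysis.

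**The concern.** There are two connected weaknesses.

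First, analysing raw change assumes that each extra point at baseline predicts exactly one extra point at week 3. At a correlation of 0.5 with equal SDs the slope is 0.5, so change carries baseline noise that ANCOVA would remove.

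Second, the other covariates are chosen by significance tests of baseline differences. Under randomisation such differences arise by chance, so the rule selects variables on chance and not on how well they predict week-3 SRRS. Baseline SRRS might count as a clinical variable under the rule, but it would enter only if it happened to differ significantly. Because the tested variables are not listed, the primary model cannot be written down until baseline data have been inspected by arm. Since the same team may already have run the primary analysis at interim looks, the list can still be open after SRRS results by arm have been seen.

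At stake are precision and a prespecified primary model. Validity of the planned test is not in question.

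**Working it through.** **1. The plan's own figure.** Inputs from 11.2: f = 0.23, N = 88, 4 groups, 2 measures, correlation 0.5, alpha 0.05. For the group-by-time test:

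λ = f² × N × 2 / (1 − ρ) = 0.0529 × 88 × 2 / 0.5 = 18.62, with F(3, 84). Power = 0.957.

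88 is the smallest multiple of four that reaches 0.95, so the stated sample size reproduces.

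**2. Adding baseline SRRS.** Set the baseline SD to 1 and let k = week-3 SD / baseline SD.

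- Variance of change: 1 + k² − 2ρk
- Residual variance under ANCOVA: k²(1 − ρ²)
- Difference: (1 − ρk)², which is never negative and is zero only when ρk = 1

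At ρ = 0.5:

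| k | Change | ANCOVA | Ratio | Saving |
|---|---|---|---|---|
| 0.8 | 0.84 | 0.48 | 0.571 | 43% |
| 1.0 | 1.00 | 0.75 | 0.750 | 25% |
| 1.3 | 1.39 | 1.2675 | 0.912 | 9% |
| 2.0 | 3.00 | 3.00 | 1.000 | 0% |

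At k = 1 the standard error falls by 1 − √0.75 = 13%. λ becomes 18.62 / 0.75 = 24.83 with F(3, 83), and power is 0.990. A simulation of 20,000 trials with 22 per arm gave 0.957 and 0.989. These are powers of the four-arm omnibus test. They do not apply to pairwise comparisons, and no power is claimed at unequal SDs.

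**3. Entry threshold.** Selecting on baseline SRRS narrows its spread and can push k above 1. Assume normal scores, equal SDs before selection, a cut applied to the baseline score itself, and a correlation of 0.5 among enrolled patients. If s² is the fraction of baseline variance left after the cut, the pre-selection ρ² is 0.25 / (0.75s² + 0.25), and k² = [1 − ρ²(1 − s²)] / s².

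| Candidates excluded | s² | k | Saving |
|---|---|---|---|
| 10% | 0.712 | 1.13 | 17% |
| 20% | 0.583 | 1.21 | 13% |
| 50% | 0.363 | 1.38 | 6% |

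Falling scores during treatment could instead push k below 1, so the direction is not known.

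**4. Other correlations.** At k = 1 the saving is (1 − ρ)/2: 35% at ρ = 0.3, 15% at 0.7 and 10% at 0.8. At k = 1.21 it is 23%, 3% and under 1%.

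**5. The conditional rule.** The number of tests is not stated, so 10 is an assumption. If the tests are independent, the chance of at least one significant result is 1 − 0.95¹⁰ = 40%. Simulation settings: 20,000 trials per setting, four arms of 22, k = 1, the planned effect placed in one arm, and 10 equally correlated baseline variables including SRRS. Every variable significant at .05 was added to the change-score model.

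| Pairwise correlation | Rule fires | Power, unadjusted | Power, rule | Power, baseline SRRS prespecified | Null rejection, rule |
|---|---|---|---|---|---|
| 0 | 40% | 95.8% | 95.8% | 99.0% | .046 |
| 0.5 | 30% | 95.7% | 96.1% | 99.0% | .043 |
| 0.7 | 23% | 95.6% | 96.2% | 99.1% | .043 |

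The rule recovers almost none of the available gain, and it does not inflate type I error when applied mechanically to a fixed list.

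**The case against.** The strongest reply is that little is at stake. The unadjusted test is valid, matches the change endpoint of 5.1 and already reaches its target power, so moving from 95.7% to 99.0% replaces an acceptable choice with a better one. That is right, and it limits how serious the point is.

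The size of the gain is also uncertain. The documents give no SDs, and the correlation of 0.5 is introduced only as moderate. Last observation carried forward (7.4 and 11.5) would tend to raise the baseline to week-3 correlation, because some patients would have their baseline score carried to week 3. Near k = 1 that shrinks the saving. All of this stands as a caution on the figure. It does not reverse the recommendation: apart from one degree of freedom, ANCOVA is not less efficient than change at any SD ratio or correlation.

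The simulation applies a fixed list of 10 variables. It does not model discretionary choice after results are seen, so it neither shows nor excludes harm from the open list. The link to the interim looks is likewise an inference, since 11.4.4 does not mention covariates. Both limits are accepted: the claim is only that the plan leaves the list open, not that bias has been shown.

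Two mitigations exist. Section 11.4.6 requires deviations from the statistical plan to be reported, and the assessment schedule in section 9.1 bounds the pool of baseline measures. Neither fixes the list, and choosing from an unlisted set would not count as a deviation.

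**Conclusion.** The concern holds. Baseline SRRS is not a planned covariate, and the primary model depends on unlisted significance tests of baseline differences. The variance lost is 25% at the protocol's correlation of 0.5 with equal SDs. With the correlation held at 0.5, it ranges from 43% down to nil as the week-3 SD goes from 0.8 to 2 times the baseline SD. It is 6% to 17% under the truncation assumptions used for the SRRS entry threshold. The power gain from 95.7% to 99.0% rests on equal SDs and concerns the omnibus test only. The firing rates of 23% to 40% rest on an assumed 10 baseline tests.

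The sample size is not wrong, the planned test is valid and no type I error inflation was shown. This is an improvement that should be made, not a defect that invalidates the trial.

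**What to change.** In 11.4.2:

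- Prespecify ANCOVA of week-3 SRRS on arm with baseline SRRS as covariate, or the equivalent baseline adjustment in a mixed model. The change endpoint of 5.1 can stay, because ANCOVA of change with baseline SRRS as covariate gives identical arm contrasts.
- Delete the rule that adds covariates when baseline differences are significant.
- Name any further covariates now, on prognostic grounds, and keep them whatever imbalance is observed.

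The text change is one or two sentences, and the baseline SRRS term costs one degree of freedom (84 to 83). SRRS is already scheduled at baseline for every patient, so no visit, measurement or patient is added and 88 can stand. Under section 2.3 the change needs prior sponsor and ethics committee approval.
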